10.6 INTERIM ANALYSIS

An interim analysis providing descriptive statistics for the outcomes may be completed following completion of the Month 6 follow-up visit by 80% of the randomized subjects. Endpoints listed below will be analyzed at an interim analysis. No device effectiveness will be claimed based on the interim analysis outcomes.

Effectiveness outcomes up to 6 months will be summarized descriptively:

1. Percent of eyes with a $\geq 20\%$ reduction in IOP with no increase in IOP-lowering medications compared to screening visit
2. Percent of eyes with IOP between 6 and 18 mmHg with no increase in IOP-lowering medications compared to screening visit
3. Percent of eyes with IOP between 6 and 21 mmHg with no increase in IOP-lowering medications compared to screening visit
4. Reduction in mean IOP from screening visit; and
5. Reduction in mean number of IOP-lowering medications from screening visit

Safety endpoints:

1. Rates of ocular adverse events (intraoperative, postoperative)
2. Reduction in BCDVA from screening (note: reduction in BCDVA due to worsening of PCO will not be treated as a safety event)
3. Secondary Ocular Surgical Interventions, including laser, for IOP control

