5.2 METHODS USED TO MINIMIZE BIAS

This study is randomized using block (a block of 6) randomization and neither the Investigator, the investigative site staff, or Sponsor clinical personnel will have knowledge of or access to the randomization scheme. Randomization to treatment group will be performed using a 1:1:1 ratio and will be stratified by site. Treatment allocation bias will thus be avoided. Once randomized into the study, the Investigator, the investigative site staff, Sponsor clinical personnel and the subject will be unmasked to the treatment assignment for each subject.

The study is multicenter with sites in at least 5 countries. The potential bias inherent in single-center trials is thus eliminated. Moreover, no site can randomize more than 25% of the study subjects. The location of sites in multiple countries incorporates greater diversity in the patient population as well as subtle geographic differences in treatment norms/standard of care allowing greater generalizability of the study results.

Mean diurnal IOP is the basis for the primary endpoint. DIOP averages three separate IOP measurements taken at different times of day. This mitigates the risk of a single measurement being unusually high or low and subsequent regression to the mean. IOP measurements will be taken using Goldmann applanation tonometry with routine and documented calibration required. IOP will be measured by 2 different study personnel (an operator and a recorder) closely following the procedure used in AGIS.¹⁹ This technique prevents unintentional bias on the part of the Investigator or technician measuring and recording the IOP.

Reintroduction and discontinuation of ocular hypotensive medications will follow a protocol defined procedure to ensure standardization across sites and remove the potential for bias in treatment regimen.

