6.2 SAFETY ENDPOINTS

- Rates of ocular adverse events (AE) (intraoperative, postoperative)
- Reduction in best corrected distance visual acuity (BCDVA) from screening
- Secondary Ocular Surgical Interventions, including laser, for IOP control

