10.5 SAFETY ANALYSIS

All safety analyses will be performed on the safety analysis population based on all available data by the three study groups separately.

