10.5.2 BEST CORRECTED DISTANCE VISUAL ACUITY (BCDVA)

BCDVA data collected at the subject Baseline, and the Week 1, 1, 3, 6, and 12 month postoperative visits. The number and percent of eyes reporting with BCDVA of 20/20 or better, 20/25 or better, 20/32 or better, 20/40 or better, worse than 20/40 to 20/80 worse than 20/80 to 20/200, and worse than 20/200 at each visit will be summarized. Also, shift tables from baseline will be presented with counts, percentages, and 95% confidence intervals.

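### Section 10.6 does not count acuity loss due to PCO as a safety event at the interim, but the synopsis, 6.2 and 10.5.2 make no such exception

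*Combined protocol and SAP*

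**What the plan says.** The safety endpoint in section 6.2 is "Reduction in best corrected distance visual acuity (BCDVA) from screening", and the synopsis has the same item. Neither names a cause that is left out.

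Section 10.5.2 gives the analysis: numbers and percentages of eyes in acuity bands at each visit, and "shift tables from baseline will be presented with counts, percentages, and 95% confidence intervals". It excludes nothing by cause. The general rule in section 10.5 is "All safety analyses will be performed on the safety analysis population based on all available data".

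Section 10.6 lists the endpoint again for the interim, with a qualifier: "note: reduction in BCDVA due to worsening of PCO will not be treated as a safety event". PCO, read here as posterior capsule opacification, appears in this connection only there in the readable text.

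On the status of the interim, section 10.6 says "An interim analysis providing descriptive statistics for the outcomes may be completed", once 80% of randomized subjects have completed Month 6. It rules out effectiveness claims from the interim and is silent on safety statements.

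On masking, section 5.2 says that after randomization the investigator and site staff, together with "Sponsor clinical personnel and the subject will be unmasked to the treatment assignment for each subject".

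**The concern.** A safety endpoint should mean the same thing each time it is reported. Here the interim version depends on a judgement about cause, and the version in 6.2 and 10.5.2 does not. A reader who compares the two reports could not tell whether a change in acuity loss reflects the eyes or the definition.

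The judgement is also open-ended. Inclusion criterion 2 requires every subject to be pseudophakic, so PCO is an available explanation in any study eye. The readable text does not say what shows that a loss is due to PCO, who decides, or whether that person knows the arm. Events set aside after such a judgement can leave the arms looking more alike or less alike than they are.

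The note also sits badly with section 9. Study-eye adverse events are to be recorded whether or not they are thought device related, and a pre-existing condition must be recorded if it increases in severity.

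**Working it through.** **1. The texts side by side**

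| Place | Treatment of BCDVA | Exception for PCO |
|---|---|---|
| Synopsis, safety endpoints | reduction from screening | none |
| 6.2 | reduction from screening | none |
| 10.5.2 | acuity bands by visit, shift tables | none |
| 10.6 (interim) | reduction from screening | yes |

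No redaction touches the BCDVA wording in these four places. The reference visit is called screening in 6.2 and 10.6 and baseline in 10.5.2. That difference is not part of the point, because section 8.4.1 says that screening data count as baseline data.

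**2. Direction of the effect**

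Let L be the eyes with a reduction from any cause, n the eyes assessed, and f the share of L attributed to PCO. Then:

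- all-cause proportion = L / n
- proportion under the 10.6 note = L(1 − f) / n

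Since f lies between 0 and 1, the second can only equal or fall below the first on the same eyes.

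**3. Size of the interim**

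The plan's total reproduces: 137 / 0.90 = 152.2, rounded up to 153 per group, and 3 × 153 = 459. The interim needs 0.80 × 459 = 367.2, so at least 368 subjects. Per group this is 0.80 × 153 = 122.4, or about 122.

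**4. Illustration (L and f are assumed)**

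The documents give no rate of acuity loss or of PCO. Take L = 12 and n = 122:

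| f | Eyes counted | Interim proportion |
|---|---|---|
| 0 | 12 | 9.8% (exact 95% CI 5.2 to 16.6) |
| 25% | 9 | 7.4% |
| 50% | 6 | 4.9% |
| 75% | 3 | 2.5% |

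An all-cause count on the same eyes gives 9.8% in every row. With L = 6, the all-cause figure is 6 / 122 = 4.9%, and at f = 50% it becomes 3 / 122 = 2.5%.

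**5. Comparison between arms**

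If two arms have the same L and n, the note creates a difference of L(f₂ − f₁) / n.

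- Equal attribution (f₁ = f₂): no difference.
- f₁ = 25%, f₂ = 75%, L = 12: 12 × 0.50 / 122 = 4.9 percentage points (9 eyes against 3).
- The same shares with L = 6: 6 × 0.50 / 122 = 2.5 percentage points.

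A gap thus appears only if attribution differs by arm, and over this range it is a handful of eyes.

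**The case against.** The strongest reply is that the two texts do not contradict each other. Section 6.2 is a single line with no threshold and no rule on cause, and 10.5.2 counts no reductions at all. The note says only that the loss is not a safety event. Under the all-available-data rule the eye could stay in the acuity tables and lose only the event label.

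Part of this stands. A reader might infer that affected eyes drop out of the BCDVA tables, or that a lower interim loss rate will later be contradicted by a final loss rate. The documents support neither: the note does not remove eyes from tables, and the readable final analysis plans bands and shifts, not a loss rate. Follow-up also differs, at Month 6 against Month 12, so the two reports could differ for that reason alone. The mismatch survives even so. The note is a stated rule, attached to the endpoint in one place and absent everywhere else.

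A reader might also infer that the protocol assigns the attribution to an unmasked investigator. It does not say who attributes. That the arm is known is a reasonable inference from 5.2 and from the lack of any named masked assessor, but it remains an inference. Part of the slit lamp appendix is redacted and section 9.2 is not visible, so a grading or criterion for PCO may exist. It would answer the question of criterion but would not reconcile 10.6 with 6.2 and 10.5.2.

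Finally, other outputs limit what could be hidden: adverse events are recorded regardless of device relation, slit lamp findings are tabulated by visit, and the final BCDVA tables exclude nothing. This is fair, and it keeps the consequence to the interim.

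**Conclusion.** The point holds as an inconsistency in a named safety endpoint. Section 10.6 carries an exception for PCO that the synopsis, 6.2 and 10.5.2 lack. Followed as written, it can only leave the interim count of acuity losses equal to or below the all-cause count on the same eyes. It does so through a judgement that is probably made with the arm known and for which no criterion can be read.

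The consequence is modest. The interim is optional and descriptive, the readable text plans no hypothesis test on BCDVA, and neither the significance level nor the sample size is affected. The final safety tables are untouched. It still deserves correction, because 10.6 restricts only effectiveness claims and the interim safety table could be read on its own.

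The size cannot be taken from the documents. The percentages above rest on assumed losses and assumed attribution shares. They show direction and scale and do not forecast what the interim will show. In particular, nothing in the documents shows that attribution would differ between arms.

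**What to change.** In section 10.6, delete the PCO note and report BCDVA reduction from screening from any cause.

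State once, for example in 6.2, what counts as a reduction, and use that definition at both the interim and the final analysis. Because 10.5.2 now plans only bands and shift tables, it needs a row for reduction under the same definition.

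If the sponsor wants the PCO split, show it as a supplementary sub-row beneath the all-cause count and never in its place. Write down the attribution criterion before the interim data are tabulated, and state who applies it and whether that person knows the arm. The sub-row rests on the same judgement, which is why it should not replace the all-cause figure.

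The cost is one deleted note, one agreed definition of reduction and one added row in the 10.5.2 tables, plus a short criterion if the split is kept. The interim figure may look slightly less favourable. No visit, measurement or sample size changes.

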10.7 DEVIATION FROM THE STATISTICAL PLAN

Any deviations from the statistical plan will be noted in the final report.

11 MONITORING PROCEDURES

Sight Sciences or contract research organization (CRO) personnel will monitor the study in a manner consistent with FDA and relevant competent authority (CA) regulations, good clinical practices and the clinical research standards adopted by Sight Sciences. Study monitoring will be executed using on-site visits, via remote means, or a combination of both, and will involve the following elements:

- **Site Qualification:** Sight Sciences or CRO personnel will meet with Investigators and clinical study staff either on site or via phone prior to the initiation of the study in order to review the adequacy of the subject population, facilities, and equipment with respect to the needs of the study, and to familiarize the Investigator with the study protocol. If Sight Sciences or the CRO have recently been involved with an Investigator for another study, a site qualification visit may not be necessary.
- **Site Initiation:** Sight Sciences and/or CRO personnel will meet with the Investigator(s) and clinical study staff when the site is ready to begin enrolling subjects in order to train them in how to properly select subjects, perform the study procedure, and record study data. This visit will include, but not be limited to a review of the following:
 - Detailed review of the protocol
 - Informed consent procedures
 - Instructions for the surgical procedure
 - Records and reports
- **Interim Monitoring:** Sight Sciences or CRO personnel will conduct routine visits either remotely or in-person, visit the clinical site as specified in the Monitoring plan during the course of the study to review charts, and to perform source document verification, to ensure proper adherence to the study protocol, and to review regulatory documents. Interim monitoring visits and telephone consultation will occur as necessary during the course of the study to ensure the proper progress and documentation of the study findings.
- **Study Closure:** At the conclusion of the trial there will be a study closure visit during which several actions, including but not limited to the following, will be performed:
 - A final inspection of the study binder
 - Accountability and return of all devices and non-consumable ancillary study supplies to the sponsor
 - Discussion of record retention requirements with the investigator
 - Close-out notification to the EC

12 DATA AND QUALITY MANAGEMENT

12.1 DATABASE MANAGEMENT

The study database will be designed using an electric data capture (EDC) system that is compliant with 21 CFR Part 11 and relevant guidance documents. The EDC will be developed and maintained by an independent, qualified EDC firm.

The database will incorporate time-stamped audit trails, protection of human subjects, restricted access, and data security at the component level. Each database module, including each individual eCRF, will be validated by conducting a series of standard tests that demonstrate usability and correctness of the database system. The database will be maintained on an ongoing basis and will be routinely backed up.

12.2 SUBJECT IDENTIFICATION

The subjects will be identified by a six-digit subject ID number composed of a two-digit study identification number, a two-digit center identification number followed by a two digit sequential subject number. The subject ID number will be assigned on subject provision of written informed consent. In this way, information contained in the study records will be de-identified and kept as confidential as possible.

12.3 SUBJECT ACCOUNTABILITY

All subjects enrolled and treated in this clinical investigation shall be monitored for the duration of the investigation. The clinical investigation shall be considered completed when all subjects that have been enrolled in the investigation have reached the final reporting period, excluding subjects who were withdrawn.

12.4 CONFIDENTIALITY

All medical records associated with the clinical investigation will be made available for review by Sight Sciences personnel, its contract research organization (CRO), contract CRAs and governmental/regulatory agencies involved. The results of the study may be published in the future for scientific and marketing purposes, but the identity (name) of each subject will not be revealed. All records will be stored in a secure area at the Investigator's facility, the CRO (if applicable), the data management firm (if applicable) and at Sight Sciences, Inc. per each organization's own SOPs and applicable data privacy laws.

12.5 SOURCE DATA AND CASE REPORT FORMS

Source data will be entered into a validated electronic system at each site by trained personnel in accordance with 21 CFR Part 11 requirements. The selective electronic entries based on pre-defined targeted SDV monitoring plan will be 100% verified against corresponding source data at the sites and queried/corrected if needed to the extent possible. Medical site records serve as source data. In addition, data that are collected exclusively for the purpose of this study and not normally recorded in the subjects' medical records can be collected directly on the study worksheets provided by the sponsor and these study worksheets will serve as the source data.

Source data and study worksheets are to be maintained at the site in the subject records or in the medical records. All data entries must be made in accordance with ALCOA (Attributable, Legible, Contemporaneous, Original, Accurate) standards and Good Documentation Practices (GDP).

12.6 RETENTION PERIOD

Clinical sites are to retain any and all clinical trial material (documentation, photographs, etc.) for a period of two years from the longer of the date the device is certified by a notified body in the EU or two years after the investigation has been discontinued, or as directed by their institutional document retention requirements, whichever is the longest. After that time, Sight Sciences must be contacted for instructions on record transfer and/ or disposition, at its discretion.

13 PROTOCOL MODIFICATIONS AND DEVIATIONS

Protocol modifications may occur during the study. Each will be approved in writing by the sponsor before implementation. Each will undergo Ethics Committee review and approval, as necessary.

Any deviations from this protocol intended to protect the life or physical well-being of a subject in an emergency are to be reported to Sight Sciences, Inc. as well as the Ethics Committee as soon as possible, and no later than 5 working days after the emergency occurred.

All protocol deviations will be documented using the Protocol Deviation form.

14 DEVICE FAILURES AND MALFUNCTIONS

All device failures or malfunctions should be recorded on the OMNI Customer Experience Form and reported to Sight Sciences.

15 ETHICAL CONSIDERATIONS

15.1 DECLARATION OF HELSINKI

This study shall be conducted in accordance with the Declaration of Helsinki (AppendixB).

15.2 RESEARCH ETHICS COMMITTEES (REC)

The protocol must be submitted for consideration, comment, guidance and approval to the concerned REC before the study begins. This committee must be transparent in its functioning, must be independent of the researcher, the sponsor and any other undue influence and must be duly qualified. It must take into consideration the laws and regulations of the country or countries in which the research is to be performed as well as applicable international norms and standards.

Copies of all written approvals (identifying the study, the submitted and approved documents and the date reviewed) and the approved versions of the documents must be provided to Sight Sciences or its agents.

The Investigators must file all correspondence with the REC and forward copies of such correspondence to Sight Sciences.

15.3 INFORMED CONSENT

Biomedical research involving interventions must not be allowed to proceed unless the potential research subject has given consent. For consent to be valid it must be informed and freely given. It includes but is not limited to: the purpose of the study, the intervention being tested, alternative treatments, that participation is voluntary, what will happen if consent is or is not granted, required study visits and other requirements for participants, that consent can be withdrawn at any time and for any reason, risks and side effects of the interventions, possible benefits from participation, confidentiality of study data, and what will happen if new information becomes available during the study. The original signed record of the consent should be kept by the Investigator as part of the study records.

An Informed Consent template that covers all protocol procedures and follows GCP Guidelines will be prepared by Sight Sciences and made available to each Investigator.

The Investigator may adapt these templates to the requirements of the local REC and of the Institution where the study is conducted, but any revisions must be submitted to the sponsor for review prior to submission to the REC. A copy of each REC-approved informed consent document is to be made available to Sight Sciences and its CRO. The approved and, REC approved informed consent document is to be kept in its full length in the study Regulatory Binder. Original, signed informed consent for each subject must be maintained in study records and must be made available for monitoring review.

15.4 PUBLIC LISTING OF STUDY

The study will be listed on the US NIH website www.clinicaltrials.gov.

16 STUDY ADMINISTRATION

16.1 EARLY TERMINATION OR SUSPENSION OF THE STUDY OR AN INVESTIGATIONAL SITE

Sight Sciences may terminate the study, in which case the Investigators and associated ECs will be notified in writing. Possible reasons for study termination include but are not limited to:

- The discovery of an unexpected, significant, or unacceptable risk to the study subjects implanted with the device
- Withdrawal from the market for either safety or non-safety reasons.
- Insufficient enrollment in the study
- The Sponsor determines that enough data has been collected for the study, and no further data are needed.

Sight Sciences reserves the right to stop the study at any site any time after the initiation visit if there have been no subject enrollments or if there have been significant protocol deviations/violations at the site.

Likewise, a principal Investigator may terminate the study at his/her institution. This decision must be followed by written notification to Sight Sciences within five working days, stating the reasons for termination.

If the study is terminated, every effort should be made to obtain final follow-up from all subjects.

In the event that there are significant human use issues with the device, the investigator will be consulted to make a determination of whether the study should be terminated or not.

16.2 INVESTIGATOR RESPONSIBILITIES

16.2.1 GENERAL RESPONSIBILITIES OF INVESTIGATORS

An Investigator is responsible for ensuring that an investigation is conducted according to the signed agreement, the investigational plan and applicable regulations, for protecting the rights, safety, and welfare of subjects under the Investigator's care, and for the control of devices under investigation. An Investigator also is responsible for ensuring that informed consent is obtained in accordance with applicable regulations.

16.2.2 SPECIFIC RESPONSIBILITIES OF INVESTIGATORS

1. Awaiting approval - An Investigator may determine whether potential subjects would be interested in participating in an investigation but shall not request the written informed consent of any subject to participate, and shall not allow any subject to participate before obtaining REC approval.
2. Subject Qualification -The Investigator is responsible for ensuring that all subjects entering the study conform to the subject selection criteria.
3. Compliance - An Investigator shall conduct an investigation in accordance with the signed agreement with the Sponsor, the investigational plan, all applicable Competent Authority regulations, and any conditions of approval imposed by an REC.

